#### 7.3.2. Baseline Characteristics

Baseline descriptive statistics on all evaluable patients will be provided on demographic variables (age, sex, race/ethnicity), ECOG performance status, laboratory parameters, the chemotherapy regimens that were previously used, the number of treatment cycles and irradiation fractions involved, and disease characteristics, including tumor size and stage.

#### 7.3.3 Analysis of Study Endpoints

Survival (LPFS, OS, TTP) will be estimated by the Kaplan-Meier method for all evaluable patients and the corresponding median survival times (with 95% confidence interval) reported. The 2-year LPFS will also be estimated along with its 95% confidence interval. The effect of variables listed in Section 7.3.2 will be explored with Cox regression models.

For the QOL data analysis, each item of the FACT-G will be individually assessed. The mean and standard deviation of the observed data will be summarized at each collection time and plotted against time, from baseline through the end of patient follow-up. Generalized linear models (such as cumulative logit models) for repeated measures will be used to explore if there are significant changes in HRQOL over time.

Using NCI Common Terminology Criteria for Adverse Events (CTCAE v4.0), the number of patients experiencing adverse events over their course of treatment will be characterized by type of adverse event and grade, by the time of onset in relation to the first day of therapy, and whether the event is clinically significant. Attribution of adverse events to treatment (unrelated, unlikely, possibly, probably, or definitely) will also be summarized for any serious adverse events (SAEs), CTCAE grade 3 or higher. The percentage of patients experiencing SAEs that are considered to be treatment-related (probable or definite) will be determined. The percentage of patients experiencing the acute and late toxicities associated with SBRT (as defined in Section 6.4) will also be estimated along with its 95% confidence interval.

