#### *1.3.1 Experience with SBRT at the University of Pittsburgh Cancer Institute*

A retrospective review from our institution evaluated the outcome in 71 subjects with intact pancreatic cancer treated with SBRT (16). With a median follow-up of 12.7 months the freedom from local progression at 6 months and 1 year was 72% and 49%, respectively. Median overall survival for the entire group was 10.3 months. Treatment-related toxicity was minimal with only 3 patients experiencing acute grade 3 toxicity (4%). There was no recorded late toxicity. We have been treating patients with close or positive margins with SBRT as well. We recently examined outcomes in 24 patients treated post-operatively with SBRT (17). Sixty-six percent of the patients had positive margins and the remainder had close margins of 1-2.5mm. The median follow-up was 1 year. The freedom from local progression at 6 months and 1 year was 95% and 66%. There was no acute or late grade 3-4 toxicity, and two patients (8%) had late grade 1-2 toxicity, again demonstrating that when done properly, SBRT has a low potential for toxicity. The current study seeks to further investigate the impact of SBRT following resection with a close or positive margin. We hope to improve local control, and through the use of a shortened treatment schedule, allow patients to begin systemic therapy earlier.

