### 6.2 Evaluation during treatment

The subjects will be carefully followed while on active treatment and post-treatment for 24 months, or until death. Evaluation during treatment will consist of the following activities:

- 6.2.1 Administration of SBRT
- 6.2.3 Interim medical history and physical examination at baseline, prior to SBRT treatment, at the end of SBRT, and 10-12 weeks after SBRT then every 3 months thereafter for up to 24 months.
- 6.2.4 Serum chemistry and electrolytes to include BUN, creatinine, sodium, potassium, bicarbonate, chloride, calcium, magnesium, glucose, total bilirubin, AST, ALT, alkaline phosphatase post-treatment as clinically indicated
- 6.2.5 Hematologic studies to include CBC with differential and platelet count prior to SBRT and repeated 10-12 weeks later and then at follow-up as clinically indicated.
- 6.2.6 CT scan will be obtained at 10-12 weeks post-treatment and will be reviewed for evidence of response. Since these subjects will likely have no gross disease on imaging, the main goal of the follow-up scans is to monitor for local and distant progression as defined below.

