#### 6.4.2. Definition Local Progression Free Survival

In this study, LPFS is defined as the time from enrollment to first documentation of progressive disease (PD) in the target lesion. Death or development of distant disease is not regarded as an event. For patients that undergo surgical resection, local progression will be defined as disease recurrence detected on follow-up imaging (CT or FDG-PET/CT) that is located within the SBRT target volume.

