#### 6.4.3 Definition of OS and TTP

TTP is defined as the time from enrollment to disease progression. Disease progression will be defined as PD in the target volume, or development of distant disease. OS is defined as the length of time from enrollment to confirmed death from any cause.

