### 7.2 Sample Size and Accrual Rate

#### 7.2.1 Sample Size

From the Investigators' treatment experience, the 2-year local progression-free survival rate for the standard of care is 40%. This phase II study aims to improve it to 60% with SBRT. We plan to have 24 months of accrual, and 24 months of follow-up beyond the last patient enrolled on study. Under assumption of exponential survival, a total of 50 patients will provide 94% power to detect a statistically significant improvement in survival by one-sided log-rank test at significance level 0.05. Assuming that there will be no loss to follow up and no ineligible case, a total of 50 patients will be accrued for this trial.

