#### 8.1.1 Subject Removal Criteria

1. Disease progression
2. Development of a serious medical illness
3. Evidence of dose-limiting toxicity
4. Voluntary withdrawal
5. Protocol violation
6. Discretion of the principal investigator
7. Development of grade 4 toxicity related to experimental therapeutic

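### LPFS is estimated only by Kaplan-Meier with deaths censored: add the cumulative incidence of local progression beside it, and restate the 94% power with deaths and follow-up length allowed for

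*Combined protocol and SAP*

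**What the plan says.** Section 6.4.2 measures LPFS from enrollment to first progression in the target lesion and adds: "Death or development of distant disease is not regarded as an event".

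Section 7.3.3 then gives the analysis: "Survival (LPFS, OS, TTP) will be estimated by the Kaplan-Meier method for all evaluable patients". It promises the median and the 2-year LPFS, each with a 95% confidence interval. Cox models are used only to explore covariates. No section mentions competing risks, cumulative incidence, or what happens to a patient who dies before local progression.

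Section 7.2.1 sets the benchmark from the investigators' experience: "the 2-year local progression-free survival rate for the standard of care is 40" (percent). The target is 60%, with 24 months of accrual and 24 months of follow-up after the last enrollment. Under exponential survival, no loss to follow-up and a one-sided level of 0.05, "a total of 50 patients will provide 94% power to detect a statistically significant improvement in survival by one-sided log-rank test".

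On follow-up per patient, section 6.2 says: "The subjects will be carefully followed while on active treatment and post-treatment for 24 months, or until death". The schedule in section 6.3 also ends at 24 months, whereas section 6.4.1 continues CT scans to the end of the study.

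**The concern.** The trial has one arm, so the absolute 2-year figure is its result. The name local progression-free survival invites two readings of that figure: that KM is the share of patients alive without local progression, and that its complement is the share who have progressed locally. With deaths censored it is neither.

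The difference matters when many patients die early, which the background leads one to expect. Sections 1.2 and 1.3 cite adjuvant-treated median OS of 19 to 25.2 months. One large trial described there had local recurrence near 25% but distant metastasis above 70%, so many deaths without local failure are plausible. The separate OS curve does not close the gap, because two marginal curves do not show the order of events within patients.

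The same censored deaths remove local events from the power calculation in section 7.2.1, which makes no allowance for them.

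**Working it through.** **Inputs from the documents.** 2-year LPFS of 40% (null) and 60% (target), n = 50, one-sided 0.05, 24 + 24 months (section 7.2.1). Median OS M of 19 months (meta-analysis, section 1.3 on chemotherapy), and 20, 21.2 and 25.2 months (section 1.2). The 25.2-month series had only R0 resections, whereas this trial enrolls close or positive margins.

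**Assumptions.** Constant, independent hazards. The hazard d of death before local failure is not in the documents, nor is any OS for post-operative SBRT, so d is bracketed.

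**Step 1: reproduce the 94%.** Monthly local-progression hazards are l0 = -ln(0.40)/24 = 0.03818 and l = -ln(0.60)/24 = 0.02128. With uniform accrual, no deaths and follow-up to study month 48, expected events at the target are 50 × [1 - (0.60 - 0.36)/(24 × 0.02128)] = 26.5. A simulated one-sample log-rank test, Z = (O - E)/√E against -1.645 (40,000 trials), gives 94% power. The stated figure reproduces.

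**Step 2: cumulative incidence at the 60% target.** 1-KM is 40% whatever d is. The cumulative incidence (CIF) is

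CIF(24) = l/(l + d) × [1 - exp(-24(l + d))],

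and the share alive without local progression is exp(-24(l + d)).

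*Upper bracket for d:* the whole OS hazard acts before local failure, d = h = ln 2/M.

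*Lower bracket for d:* deaths by 24 months cannot exceed all patients who have either progressed locally or died first, 1 - exp(-24(l + d)). To match the 1 - exp(-24h) dead that OS implies, d must be at least h - l. At that minimum, CIF = (l/h) × [1 - exp(-24h)].

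Example, M = 19: h = 0.03648. Upper bracket: 0.02128/0.05776 × (1 - 0.250) = 27.6%. Lower bracket: d = 0.0152, CIF = 0.5834 × 0.5834 = 34.0%.

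| Median OS (months) | Dead by 24 months | CIF, full hazard (gap to 40%) | CIF, smallest feasible hazard (gap) | Alive without local progression |
|---|---|---|---|---|
| 19 | 58.3% | 27.6% (12.4) | 34.0% (6.0) | 25.0-41.7% |
| 20 | 56.5% | 28.1% (11.9) | 34.7% (5.3) | 26.1-43.5% |
| 21.2 | 54.4% | 28.6% (11.4) | 35.4% (4.6) | 27.4-45.6% |
| 25.2 | 48.3% | 30.1% (9.9) | 37.4% (2.6) | 31.0-51.7% |

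The smallest feasible hazard is an extreme case: it requires every patient with local progression to be dead by 24 months. Of 50 patients, about 12.5 (50 × 0.250) to 25.8 (50 × 0.517) would still be at risk at 24 months.

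**Step 3: power with deaths censored.** Same test and simulation; ranges run over the four medians.

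| Deaths before local failure | Follow-up to study month 48 | Follow-up stops at 24 months per patient |
|---|---|---|
| None | 94% (26.5 events) | 88% (20.0 events) |
| Smallest feasible hazard | 89-92% (21-24 events) | 83-86% (17-19 events) |
| Full OS hazard | 80-84% (16-18 events) | 75-79% (14-15 events) |

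A formula based on the 30 events expected by 24 months under the null (50 × 0.60) also returns 94%: √30 × 0.584 - 1.645 = 1.555, where 0.584 = |ln(0.02128/0.03818)|. It does not rescue the figure, because simulation under that follow-up gives 88%.

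**The case against.** The strongest reply is that nothing in the planned estimate is wrong, and that stands. Section 6.4.2 says openly that death is not an event, and KM with deaths censored suits that definition as a net quantity. For a local treatment, net local control is a defensible target. The institution's own post-operative series is reported in similar terms: "The freedom from local progression at 6 months and 1 year was 95% and 66" (percent). The one-sample log-rank test is not invalidated by the censoring. Section 7.3.3 promises a 2-year LPFS, not a share who progress locally, so any harm comes through misreading.

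It is also fair that the gap rests on an assumed hazard, and that cumulative incidence has a weakness of its own: it falls when early deaths rise and can flatter a treatment.

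What remains is narrower. The censoring rule and its independence assumption are not stated, the endpoint's name encourages the misreading, and no planned output gives either patient-level share. The direction does not depend on the assumed hazard: whenever some patients die first, 1-KM exceeds the cumulative incidence.

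A reader might also infer that the 40% benchmark is on a different scale from the trial estimate. The documents do not support that, because section 7.2.1 does not state the benchmark's scale.

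**Conclusion.** The point holds as a cheap improvement to reporting, not as an error in the primary estimate. At the 60% target, 1-KM exceeds the 24-month cumulative incidence of local progression by about 5-12 points for median OS of 19-21.2 months, and by about 3-10 points at 25.2 months. This rests on independent exponential hazards and on OS borrowed from other adjuvant populations. The 25.2-month figure is the least comparable, being from an all-R0 series.

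The 94% power is arithmetically reproducible, so a reader should not infer a calculation error. It is conditional on no deaths and on following patients to study month 48. With deaths censored, power is about 80-84% at the full OS hazard and 89-92% at the smallest hazard consistent with OS. If follow-up ends at 24 months per patient, it is about 88% without deaths and 75-86% with them.

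A reader might extend the point to TTP, which also omits death ("Disease progression will be defined as PD in the target volume, or development of distant disease"). No size can be put on that from the documents, and no change is asked for there. Nor does the endpoint need renaming, provided the censoring rule is stated.

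**What to change.** In section 7.3.3, keep KM with deaths censored as the estimate on the 40%/60% scale. State that deaths without local progression are censored, and that the net reading assumes death is independent of local failure. Beside it, report the 24-month Aalen-Johansen cumulative incidence of local progression, with death without local progression as a competing event, its 95% confidence interval and the number at risk. State the scale of the 40% benchmark and compare it only with the estimate on that scale.

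In section 7.2.1, restate the power with deaths censored, and say whether patients are followed to study month 48 or for 24 months each.

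The cost is a paragraph in each section and one standard analysis. It needs dates of local progression and death, which follow-up under section 6.2 would supply. Section 8.1.1 lists "1. Disease progression" as a removal criterion, so the two sections should be reconciled on whether data collection continues after distant progression; both estimators depend on it. The downside is a second 2-year figure to explain, and the cumulative incidence must be read together with OS because it falls when early deaths rise.

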#### *5.3 On-Treatment assessment and post-treatment toxicity evaluation*

All subjects will be seen prior to delivery of each fraction of SBRT with toxicity evaluated by physical examination. Subsequently, subjects will be evaluated for toxicity 10-12 weeks later and then every 3 months until at least 2 years. Toxicities will be scored by the NCI CTC AE version 4.0. Also see Section 6.0.

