### 6.3 Treatment schedule

Parameter	Pre-Study	SBRT			10-12 weeks post-treatment	Q 3 months until 24 months
		Fx 1	Fx 2	Fx3		
History	X	X		X	X	X
Physical exam	X	X		X	X	X
Measurement of disease	X				X	X
Performance Status	X				X	X
Serum Chemistry	X*				X ▲	X ▲
Hematologic Studies including CBC	X*				X	X ▲
CT Scan	X				X	X Ω
Serum or Urine Pregnancy Test for WOCBP	X					
Histologic and Morphologic Confirmation and Margin Status	X					
QOL assessment	X				X	X

\* Within 30 days of study start

▲If clinically indicated

ΩMay be modified by oncology team if patient receives system therapy

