### 6.4 Post-treatment evaluation and plan

#### 6.4.1 Evaluation of CT Imaging

A follow-up CT scan will be obtained at 10-12 weeks post-SBRT and then every 3 months until end of study. If the patient goes on to receive systemic therapy, the follow-up CT schedule can be modified at the discretion of the oncology team.

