## 7.0 STATISTICAL CONSIDERATIONS

### 7.1 Study Objectives and Design

The primary objective is to determine the LPFS in subjects with resected pancreatic adenocarcinoma with close or positive margins treated with SBRT. Secondary objectives include the evaluation of TTP, OS, acute and late toxicities, and QOL. These study endpoints are defined in Section 6.4.

This clinical trial is planned as a prospective single-arm phase II study. The treatment schema is shown in Section 6.3a.

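### Section 7.3.3 omits the one-sided log-rank test on which Section 7.2.1 bases N = 50, and the stated 94% power falls to 88% if follow-up ends at 24 months per patient, and lower if deaths censor LPFS

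*Combined protocol and SAP*

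**What the plan says.** Section 7.1 states the design: "This clinical trial is planned as a prospective single-arm phase II study". Section 7.2.1 takes a 2-year LPFS of 40% under standard care, aims for 60% with SBRT, assumes exponential survival, and claims for 50 patients "94% power to detect a statistically significant improvement in survival by one-sided log-rank test at significance level 0.05". It assumes no loss to follow-up and no ineligible case. It makes no mention of deaths.

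The analysis section, 7.3.3, plans Kaplan-Meier curves and medians with confidence intervals for LPFS, OS and TTP, and exploratory Cox models. On the 2-year rate it says: "The 2-year LPFS will also be estimated along with its 95% confidence interval". It gives no log-rank test, no 40% reference, no significance level and no criterion for success.

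On follow-up, Section 7.2.1 says: "We plan to have 24 months of accrual, and 24 months of follow-up beyond the last patient enrolled on study". Section 6.2 says: "The subjects will be carefully followed while on active treatment and post-treatment for 24 months, or until death". The last column of the schedule in Section 6.3 is headed "Q 3 months until 24 months". Objective 2.1 also speaks of two years of follow-up. Section 6.4.2 defines LPFS by local progression alone, so neither death nor distant disease is an event.

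**The concern.** There are two linked problems.

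First, the comparison that justifies the sample size has no counterpart in the section that says what will be analysed. A reader of Section 7.3.3 cannot tell how the result will be judged against 40%, at what level, or with which data cut-off. That leaves room to choose the comparison after the data are seen.

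Second, the quoted power depends on how long patients are observed and on how many die before local progression. If earlier-enrolled patients stop at 24 months, or if deaths remove patients from risk, there are fewer local events than 94% power needs. The background sections cite median survivals of about 11 to 25 months in resected patients, so many deaths within the observation window are plausible.

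**Working it through.** **Inputs from Section 7.2.1:** null 2-year LPFS 40%, target 60%, exponential, n = 50, one-sided 0.05, 24 months of accrual plus 24 months after the last patient.

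**Hazards.** Null: −ln(0.4)/24 = 0.0382 per month. Target: −ln(0.6)/24 = 0.0213 per month. Hazard ratio 0.0213/0.0382 = 0.557, log −0.584.

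**Which test.** With one arm, the log-rank must be the one-sample version: Z = (O − E)/√E, where O is the number of local progressions and E is 0.0382 times total patient-months at risk. Success is Z < −1.645. Two-arm readings do not give the plan's figure: 25 per arm gives 50% power and 50 per arm gives 75%.

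**Expected events with no deaths.**
- Follow-up uniform over 24 to 48 months: 50 × [1 − (S(24) − S(48))/(24λ)]. Target: 50 × [1 − (0.60 − 0.36)/0.511] = 26.5. Null: 50 × [1 − (0.40 − 0.16)/0.916] = 36.9.
- Follow-up of 24 months for everyone. Target: 50 × 0.40 = 20. Null: 50 × 0.60 = 30.

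**Reproducing the 94%.** Simulating the test (100,000 trials) with 24 to 48 months and no deaths gives 94.1% to 94.2%, with an actual one-sided size of about 4.2%. The plan's figure is reproduced.

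**Changing follow-up and adding deaths.** The documents give no rate of death without local progression. The last three rows therefore rest on an assumption: exponential deaths, independent of local progression, censor LPFS. The medians 25.2 and 20 months come from Section 1.2, and 14 months from the section on chemotherapy alone. All three are from other regimens and populations, and the 25.2 is from an R0-only series.

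| Censoring by death | Power, 24–48 months (events) | Power, 24 months (events) |
|---|---|---|
| None | 94% (26.5) | 88% (20.0) |
| Median OS 25.2 months | 84% (17.8) | 78% (15.1) |
| Median OS 20 months | 81% (16.3) | 76% (14.1) |
| Median OS 14 months | 75% (13.7) | 70% (12.3) |

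**A caution on the formula.** Section 7.2.1 does not name its power formula. One approximation uses the log hazard ratio with the events expected under the null. At 24 months per patient it gives √30 × 0.584 − 1.645 = 1.555, that is 94.0%. On the stated accrual and follow-up it gives √36.9 × 0.584 − 1.645 = 1.90, that is 97%. So 94% might have been obtained for a 24-month design, but the simulated power of the test itself in that design is 88%.

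**The case against.** Section 7.2.1 belongs to the same statistical chapter and already gives the endpoint, test, side, level, reference rate and distribution. The primary objective is to determine the LPFS rate, and Section 7.3.3 does estimate it. On this view only a sentence carrying the test over is missing. That is fair, and it limits the severity, but the sentence is still needed.

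Several stronger readings are tempting and are not supported:

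- *The 95% interval is the success rule, with less power than 94%.* No section says that the interval decides success. It is an estimate, and power calculated for it would describe a rule the plan does not contain.
- *The 94% is a miscalculation, or can arise only with 24 to 48 months.* It reproduces under the assumptions of Section 7.2.1, and one approximation also gives it at 24 months.
- *All the follow-up statements conflict.* Section 5.3 ("subjects will be evaluated for toxicity 10-12 weeks later and then every 3 months until at least 2 years") and Section 6.4.1 ("A follow-up CT scan will be obtained at 10-12 weeks post-SBRT and then every 3 months until end of study") are both compatible with Section 7.2.1. The tension is between Sections 6.2 and 6.3 and Section 7.2.1. Even there, the phrase about the last patient may mean only that the study closes when that patient reaches 24 months. On that reading every patient may have only 24 months, and the 88% applies.
- *Deaths will reduce power to a known figure.* The size rests on assumed independence and on borrowed survival medians. Rare deaths without local progression would cost little. The lowest cited median, 11 months in a surgery-only arm, would cost more than the range shown.
- *The trial is too small.* No section makes 94% a required minimum, and most of the less favourable figures remain near or above 80%.

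One further objection stands in part. The test depends on the exponential shape of the null curve. As an illustration, take the institution's post-operative SBRT cohort in Section 1.3.1 (95% free of local progression at 6 months, 66% at 12) and assume that it falls to exactly 40% at 24 months. The test then rejects in about 7% to 8% of trials with 24 months of follow-up and about 5.5% with 24 to 48 months, against about 4.2% under an exponential null.

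**Conclusion.** The concern holds in this form. The text alone shows that the test and decision rule behind N = 50 are absent from Section 7.3.3. The drop from 94% to 88% needs no assumption about deaths and follows if the 24-month schedule of Sections 6.2 and 6.3 governs. The further drop, to about 75% to 84% with 24 to 48 months or 70% to 78% with 24 months, is conditional on independent death censoring with median OS of 14 to 25.2 months. The stated power is therefore the favourable end of what the schedule and endpoint definition allow. This should be corrected, but it does not show that the design is inadequate.

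**What to change.** In Section 7.3.3, name the Section 7.2.1 test as the primary comparison: a one-sample log-rank test of LPFS against the exponential curve with 40% at 24 months, one-sided 0.05, with success if significant. State that patients who die without local progression are censored at death, and give the data cut-off. Keep the 2-year Kaplan-Meier rate and its confidence interval as estimation.

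Reconcile the per-patient follow-up in Sections 6.2 and 6.3 with Section 7.2.1. Then restate the power in Section 7.2.1 for the reconciled follow-up, and again under a death-censoring assumption labelled as such, naming the method used.

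The cost is wording in a few sections and a less favourable power statement. If the longer follow-up is adopted, earlier-enrolled patients need assessments beyond 24 months. Making the test primary also ties the conclusion to an exponential null shape, so the 2-year rate should be reported against 40% as a supportive check. No change in sample size is required.

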### *Secondary*

2.2 To determine the time to progression (TTP) and overall survival (OS) in this patient population

2.3 To evaluate the impact of SBRT on the QOL of subjects in the adjuvant setting

2.5 To evaluate the acute and late toxicities associated with SBRT for pancreas cancer

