#### *6.4.4 QOL evaluation*

QOL evaluation will be carried out according to the treatment schema in section 6.0. The survey will be the FACT-G and will be administered prior to SBRT, after completion of SBRT, and at each follow-up. See appendix A for more details.

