**PHYSICAL WELL-BEING**

		Not at all	A little bit	Some-what	Quite a bit	Very much
GP1	I have a lack of energy.....	0	1	2	3	4
GP2	I have nausea .....	0	1	2	3	4
GP3	Because of my physical condition, I have trouble meeting the needs of my family .....	0	1	2	3	4
GP4	I have pain .....	0	1	2	3	4
GP5	I am bothered by side effects of treatment .....	0	1	2	3	4
GP6	I feel ill .....	0	1	2	3	4
GP7	I am forced to spend time in bed .....	0	1	2	3	4

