**SOCIAL/FAMILY WELL-BEING**

		Not at all	A little bit	Some-what	Quite a bit	Very much
GS1	I feel close to my friends .....	0	1	2	3	4
GS2	I get emotional support from my family .....	0	1	2	3	4
GS3	I get support from my friends.....	0	1	2	3	4
GS4	My family has accepted my illness .....	0	1	2	3	4
GS5	I am satisfied with family communication about my illness.....	0	1	2	3	4
GS6	I feel close to my partner (or the person who is my main support).....	0	1	2	3	4
Q1	Regardless of your current level of sexual activity, please answer the following question. If you prefer not to answer it, please mark this box  and go to the next section.					
GS7	I am satisfied with my sex life.....	0	1	2	3	4

Please circle or mark one number per line to indicate your response as it applies to the past 7 days.

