**EMOTIONAL WELL-BEING**

		Not at all	A little bit	Some-what	Quite a bit	Very much
GE1	I feel sad .....	0	1	2	3	4
GE2	I am satisfied with how I am coping with my illness .....	0	1	2	3	4
GE3	I am losing hope in the fight against my illness .....	0	1	2	3	4
GE4	I feel nervous .....	0	1	2	3	4
GE5	I worry about dying .....	0	1	2	3	4
GE6	I worry that my condition will get worse .....	0	1	2	3	4

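### FACT-G is to be analysed item by item over 27 items with no prespecified domain or total score; adding summary scores beside the items is a cheap, minor improvement, and the timing wording in 6.4.4 needs clarifying

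*Combined protocol and SAP*

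**What the plan says.** Secondary objective 2.3 is "To evaluate the impact of SBRT on the QOL of subjects in the adjuvant setting". Section 7.3.3 holds the only QOL analysis text. The unit of analysis is the single item: "each item of the FACT-G will be individually assessed". The descriptive part reads "The mean and standard deviation of the observed data will be summarized at each collection time", plotted from baseline to the end of follow-up. Generalized linear models for repeated measures, with the cumulative logit model as the example, "will be used to explore if there are significant changes in HRQOL over time".

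Appendix A prints the FACT-G under four domain headings, each item scored 0 to 4, without scoring instructions. Item wording runs in both directions. All the physical items are negative, for example "I have a lack of energy". The emotional items are negative except GE2, "I am satisfied with how I am coping with my illness". GS7 may be declined: "If you prefer not to answer it, please mark this box".

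On timing, section 3.4 places the form before treatment and at each follow-up visit. The 6.3 table marks QOL at pre-study, at 10-12 weeks and every 3 months to 24 months. Section 6.4.4 begins "QOL evaluation will be carried out according to the treatment schema in section 6.0" and then names three occasions: before SBRT, once SBRT is finished, and each follow-up.

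**The concern.** A reader of the final report will want to know whether quality of life got better, worse or stayed the same. As written, the plan commits to 27 separate answers and to no overall one. If a few items move, nothing prespecified shows whether that is chance, a symptom effect or a general change, and the choice of which items to stress would be made after the data are seen.

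What is at stake is the interpretation of one exploratory secondary endpoint. No QOL error rate is stated, no stopping or success rule uses QOL, and the primary endpoint is unaffected.

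The schedule wording raises a smaller question. Sites need to know whether a form is due soon after the last fraction. The form asks about the past 7 days, so one that was intended but not collected cannot be recovered later.

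**Working it through.** The plan gives no QOL sample size, power, significance level or expected change, so there is no QOL figure of its own to reproduce.

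**Inputs from the documents**
- Items in Appendix A: 7 physical + 7 social/family + 6 emotional + 7 functional = 27.
- Negative wording: GP1-GP7 (7) plus GE1 and GE3-GE6 (5) = 12. Positive wording: 27 - 12 = 15.
- Patients: 50 (4.1.1 and 7.2.1), the most paired forms possible.

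**Assumptions, not in the documents**
- One two-sided test at 0.05 per item.
- Equal correlation r between all items.
- A paired normal approximation in place of the cumulative logit model.
- For power, a shift of 0.25 SD of change in each affected item.

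**1. Chance findings when nothing changes**
- Expected number: 27 x 0.05 = 1.35, whatever the correlation.
- At least one, if items were independent: 1 - 0.95^27 = 0.750.
- At least one, with equicorrelated normal statistics (numerical integration): 0.630, 0.483 and 0.326 at r = 0.3, 0.5 and 0.7.
- At least one of five summaries (four domains and the total, by simulation): about 20% at r = 0, and 12%, 10% and 8% at r = 0.3, 0.5 and 0.7.

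**2. What summary scores gain and lose (n = 50)**

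With k items shifted inside a score of m items, the mean of the test statistic is k x 0.25 x sqrt(50) / sqrt(m(1 + (m - 1)r)).

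- One shifted item on its own: 0.25 x 7.071 = 1.768, power 42%.
- All seven physical items shift, r = 0.5. Physical domain: 12.374 / sqrt(7 x 4) = 2.34, power 65%. Total: 12.374 / sqrt(27 x 14) = 0.64, power 10%.
- Two physical items shift, r = 0.5. Physical domain: 3.536 / sqrt(28) = 0.67, power 10%. Total: 3.536 / sqrt(378) = 0.18, power 5%.

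| Shift | Measure | r = 0.3 | r = 0.5 | r = 0.7 |
|---|---|---|---|---|
| 7 physical items | physical domain | 80% | 65% | 54% |
| 7 physical items | total | 13% | 10% | 8% |
| 2 physical items | physical domain | 13% | 10% | 9% |
| 2 physical items | total | 6% | 5% | 5% |
| any shifted item | that item alone | 42% | 42% | 42% |

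The domain score does better than a single item when the whole domain moves. The single item does better when only two symptoms move. The total alone is weak in both cases.

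**3. Precision of a mean change**

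The 95% half-width is t(0.975, n - 1) / sqrt(n): 0.28 SD of change with 50 forms and 0.37 SD with 30. The number of completed forms therefore needs to be reported.

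**4. Schedule passages side by side**
- 6.4.4 names three occasions and the QOL row in 6.3 has three marks. They can be matched one to one, with the form after SBRT taken as the 10-12 week form. Section 3.4 fits that reading.
- Against it, 6.2.3 treats the end of SBRT and 10-12 weeks after SBRT as different times, and 6.4.4 lists its form after SBRT apart from follow-up.
- Neither argument settles which was meant.

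**The case against.** The best defence is that item-level analysis is a reasonable choice here. Section 5.4 lists fatigue, abdominal pain and nausea among the short-term effects of SBRT, and these correspond closely to GP1, GP4 and GP2. If only two such symptoms moved, each item would have 42% power against 9-13% for the domain score and 5-6% for the total. This stands. It is why the items should stay in the analysis, and why a reader who concludes that item tests ought to be dropped or barred from any claim would go too far.

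Three further points also stand. First, the model sentence in 7.3.3 speaks of HRQOL over time and does not restrict its outcome to single items. One might infer that a summary score is ruled out; the text shows only that none is prespecified. Second, items analysed one at a time need no reverse-scoring and no rule for an unanswered GS7, so those gaps matter only once scores are formed. Third, the plan says it will explore, and it sets no QOL level. The 75% figure for at least one chance finding depends on independence and falls to 33% at r = 0.7; it should not be read as the plan's error rate.

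What the defence does not answer is that a named secondary objective has no prespecified overall result, although supplying one needs only data already collected.

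**Conclusion.** The point holds as a minor, low-cost improvement. Section 7.3.3 prespecifies 27 item analyses and no domain or total score, so objective 2.3 lacks a prespecified summary result. About 1.35 items would be expected to look significant by chance, given one two-sided 0.05 test per item and no true change. That count does not depend on correlation, but it does depend on the assumed level. The power figures rest on the assumed 0.25 SD shift, equal correlations and complete forms from all 50 patients; they show a trade-off between items and summaries and do not predict results.

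A reader might also infer that the sections contradict each other on a form after SBRT. The documents do not establish that. The wording in 6.4.4 allows either the 10-12 week form or an additional one, which supports a request to clarify and adds no weight to the analysis point.

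Better scores would not show the effect of SBRT either. This is a single arm, and section 3.5 permits systemic therapy after SBRT, so change over time cannot be attributed to SBRT alone.

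**What to change.** **In 7.3.3**
- Add the four FACT-G domain scores and the total as the prespecified QOL summaries. State that negatively worded items are reverse-scored, and how a score is formed when an item such as GS7 is unanswered.
- Report change from baseline with 95% confidence intervals from the repeated-measures model at one named visit already in the schedule, for example 10-12 weeks. Give the number of completed forms at every visit, because the means use observed data only.
- Keep the planned item analyses beside the summaries, labelled exploratory, and state that 27 items were examined.
- Say that change over time in one arm, with systemic therapy permitted, does not isolate an SBRT effect.

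**In 6.4.4**
- State whether the form after SBRT is the 10-12 week form or an additional one, and bring 3.4, 6.3 and 6.4.4 into line. If it is additional, show it in the table with its timing.

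**Cost.** The analysis change is a few sentences and needs no new data. Its downside is dilution: the total dilutes a change confined to one domain, and a domain score dilutes a change in one or two symptoms. Keeping domains, total and items together limits that. The schedule change is wording only if no extra form is meant. Otherwise it adds one form per patient and possibly a contact after the last fraction, since 6.2.3 plans only history and physical examination at the end of SBRT.
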